After signing informed consent, all subjects will complete a basic information questionnaire. The questionnaire will survey the frequency of wheelchair usage, transfers, percentage of non-level transfers, basic demographics (age, gender, years since SCI, etc.), work history, history of medical problems, current medications, and alcohol and smoking usage.

Pain and Health Measures

Numerical rating scale (NRS): Subjects will complete this scale once for each upper limb joint (wrist, elbow, and shoulder). The subjects will be asked to rate their average, most severe, and least severe wrist, elbow or shoulder pain during the past 24 hours using an 11-point scale (i.e. 0-10) anchored at the ends by "no pain" and "worst pain ever experienced." An 11-point NRS measure of pain intensity allows for comparison across clinical trials of pain treatment and is recommended as a core outcome measure for chronic pain clinical trials. NRS pain measures are widely used and have been shown to be valid and reliable assessments of pain.

WUSPI – Wheelchair User's Shoulder Pain Index: The WUSPI is a 15-item, self-report instrument that measures shoulder pain intensity, within the last week, in wheelchair users during various functional activities of daily living, such as transfers, loading a wheelchair into a car, wheelchair mobility, dressing, bathing, overhead lifting, driving, performing household chores, and sleeping. The WUSPI is a valid and reliable measure of shoulder pain. This survey asses the previous tasks over the time span of the week leading up when the survey was being answered. Test-retest reliability of the total index score was 0.99 and Cronbach's alpha (internal consistency) was 0.98.

Carpal Tunnel Syndrome Self-Report Questionnaire: This self-report instrument includes two scales: a Symptom Severity Scale consisting of 11 questions and a Functional Status Scale evaluating 8 different activities. This instrument is reproducible, internally consistent, and responsive to clinical changes in symptoms.

Vibration Tolerance: Participants will be screened for their tolerance to the feeling of the vibration prior to collecting the biomechanics outcome measures. Participants will hold the dumbbell at 25Hz for 30 seconds with their arm at a forty-five-degree angle away from their bodies (position similar to a bicep curl). If they are unable to complete the assessment they will not be permitted to continue the study.

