If subjects successfully complete the vibration screening they will continue with the following assessments during Visit 1:

General Health and Function: The 36-Item Short Form Health Survey Walk Wheel (SF-36 WW) is a slightly modified version of the original SF-36 that has been validated for persons with SCI. The SF-36 is a brief, multi-dimensional, self-report health questionnaire that measures eight concepts - Physical Functioning,

Role limitation due to Physical problems, Bodily Pain, General Perception of Health, Vitality, Social Function, Role limitation due to Emotional problems, and Mental Health. The domain scales ranges from 0 (worst possible health state measured by the questionnaire) to 100 (best possible health state).

Power output: the Lode Arm Ergometer will be used to measure the maximum power output for each participant. This test will be done with the participant seated in their wheelchair. The arm ergometer height will be adjusted such that participants are able to comfortably reach and crank both pedals. Additionally, we will want subjects to be in a stable participation. If they are able to, participants should brace their feet on their foot plate. If a participant does not feel enough stability in their wheelchair we will have a stable chair for them to transfer to in order to perform the evaluation. Participants will start out by cycling on the arm ergometer at a comfortable pace as a warm up. Once the participant feels as though they are sufficiently warmed up the test will begin. Participants will begin cycling against maximum resistance. Once that happens participants will be instructed to cycle as hard and as fast as they can for as long as they are able to. Once they are no longer able to crank against the resistance the test will stop and the maximum resistance will be recorded. We will complete this process three separate times, with a minimum of 30 seconds of rest in between. After the test is completed, the resistance will return to zero and the participants will cycle at a comfortable pace to cool down. They will cycle as long as they need to in both the warm up and cool down phases.

Muscle Strength Testing

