Isokinetic strength measurements will be recorded at a torque arm speed of 60 deg/sec using an instrumented dynamometer (BiodeX Medical System, New York, USA). The torque measurements will be recorded in a randomized fashion for both arms for the following test maneuvers: shoulder flexion/extension in the sagittal plane (-30 to 50 degrees), shoulder abduction/adduction in the frontal plane (10 to 70 degrees), shoulder internal/external rotation in the transverse plane (0 to 45 degrees), elbow flexion/extension (0 to 90 degrees), forearm supination/pronation (-80 to 80 degrees) and wrist flexion/extension (-45 to 45 degrees) and grip strength. One trial of 5 practice repetitions for each movement tested will be completed prior to data collection. In order to ensure the maximal force production of the tested upper extremity subjects will be secured into the chair with three padded belts: two diagonally across their chest and one across their lap. After the practice trial, one trial of five repetitions will be recorded for each muscle group. In between the practice trial and data collection trial, participants will rest a minimum of 60 seconds and in between each muscle groups participants will rest a minimum of 2 minutes. Participants may request additional time as needed. After completing all the strength testing subjects may rest before performing the functional tests.

Functional Testing

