All subjects' one rep maximum (1RM) for each of the exercises to be performed in the training phase will be determined at their baseline visit with a non-vibrating dumbbell in accordance with standard procedures. The following exercises will be tested for a one rep max as well as will be performed during the study: butterflies, serratus punches, side flies, straight arm rows, bicep curls, internal and external rotation, front raises, triceps extension, and bent over rows. Pictures of each exercise can be found in other attachments. Dumbbell weight will be increased accordingly until the subject reaches their 1 RM. If a subject is not able to perform a 1RM with the dumbbell for a given exercise, they will start their training protocol using a lower weight dumbbell for that exercise until they can hold the vibrating dumbbell for 30 seconds.

After the standard 1RM test, subjects will receive education and instructions on the use of the vibrating dumbbell. They will start with holding the dumbbell at a moderate frequency (25 Hz) and experience how the effects of the vibration on the arm and body can change with differing arm positions and grips. They will be instructed to grip the dumbbell as hard/tightly as possible throughout the course of training in order to concentrate the vibrations to the arm muscles and surrounding structures. Subjects will receive a pair of gloves to aid in maintaining a strong, firm grip during the exercises. These gloves will be for the personal use of each participant during the testing and will be theirs to keep at the conclusion of the study. Starting with the biceps curl exercise to demonstrate what higher vibrations feel like, subjects will hold the bicep curl in the static training posture (90 degrees of elbow flexion, 60% 1 RM) while the frequency is progressively increased to 40 Hz. They will be asked to hold the position for as long as they can until they reach a pain-free level of muscle exhaustion. This same process will be repeated for all the exercises to ensure they can tolerate each position at 40 Hz. If they can hold the position for an exercise for longer than 60 seconds at 40 Hz, weight will be added to the dumbbell (see below Training Intensity Assessment and Adjustments). If a subject is unable to tolerate 40 Hz for any one of the exercises, they will start that exercise in their first training session at 30 Hz, the minimum frequency for

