use another surface in their home for these exercises if it is determined to be safe and appropriate by the trainer or other member of the study team. For the rest of the exercises, subjects will exercise while in their wheelchair. A lap belt will be provided to subjects who do not have one and will be used to secure their pelvis in the wheelchair and to provide a more stable base of support while exercising. Emphasis will be placed on maintaining a neutral thoracic and cervical posture and avoiding scapular elevation during seated exercises. Depending on the amount of trunk control present, subjects may use their opposite limb to brace their trunk (either forearm pressed against their thighs or placed on an adjacent table) for exercises involving forward trunk flexion (e.g. bent over rows, triceps extensions and side flies). Verbal cuing and spotting from the trainer will be provided during the sessions to monitor positioning and safety with the exercises.

The trainer will only facilitate and supervise the exercise training. The trainer who will be conducting the training sessions will guide the subjects through each exercise set and ensure that the correct weights, timing, vibration frequency, arm postures and technique are being used to maximize subject safety. He/she will also perform survey-based data collection and research procedures. Training procedures will be stopped immediately by the trainer if a subject complains of pain or extreme discomfort during the exercises. The subject will be instructed to check in with his/her physician before resuming training.

The trainer will reassess the intensity of the training parameters at the end of each session and adapt as necessary. He/she will keep a training log for each subject and session that documents the training parameters (e.g. hold times completed each session), total session duration time, and changes made to increase/decrease efforts for the next session. Health parameters, such as heart rate and blood pressure will be collected. An automatic blood pressure monitor will be placed on the upper arm of the subject to measure their blood pressure. An automatic pulse ox monitor will be placed on the finger of the subject to measure their heart rate. The trainer will also take general notes on the sessions and the exercises, as well as the plan for the next exercise session.

Each training session is expected to take up to 1.5 hours.

Training Intensity Assessment and Adjustments

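### The protocol describes no blood pressure or heart rate reading before the maximal efforts at the lab visits, and no value read in training requires action

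*Combined protocol and SAP*

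**What the plan says.** The training-session text, which precedes Training Intensity Assessment and Adjustments, states: "Health parameters, such as heart rate and blood pressure will be collected". It names an automatic arm cuff and a finger pulse oximeter. The same text gives the safety stop: "Training procedures will be stopped immediately by the trainer if a subject complains of pain or extreme discomfort during the exercises". The subject is then told to see a physician before training resumes.

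Visit 1 has one same-day gate, under Vibration Tolerance, a 30-second hold at 25 Hz: "If they are unable to complete the assessment they will not be permitted to continue the study". It tests tolerance of the vibration only.

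The maximal efforts of Visit 1 follow that gate. Under Power output, "participants will be instructed to cycle as hard and as fast as they can for as long as they are able to"; the end point is "Once they are no longer able to crank against the resistance the test will stop and the maximum resistance will be recorded"; and "We will complete this process three separate times, with a minimum of 30 seconds of rest in between". Under Muscle Strength Testing, "After the practice trial, one trial of five repetitions will be recorded for each muscle group", for both arms. The text after Transfer Assessment adds a 1RM test for each exercise, then a 40 Hz biceps hold to exhaustion: "This same process will be repeated for all the exercises to ensure they can tolerate each position at 40 Hz".

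Visit 2 repeats the strength test. Visit 3 repeats the strength, power and functional measures.

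**The concern.** The protocol plans to measure blood pressure and heart rate, but does not link a reading either to the hardest efforts or to a decision.

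At the lab visits, the physician release and the medical history describe the subject before the day of testing. Neither shows the resting state that day. An ergometer bout has only one written end point, inability to keep cranking. Perceived exertion is recorded for propulsion and transfers, not for the ergometer, strength or 1RM tests.

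In training, a reading is taken, but an abnormal value without symptoms need not change anything that day. Sessions normally take place at the subject's home with a trainer, and the senior review need be only weekly.

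What is at stake is participant safety during testing and training. The strength, function and pain results do not depend on it.

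**Working it through.** The plan states no figure to reproduce. The check is to read the protocol for every mention of blood pressure, heart rate, limits, stopping and withdrawal, and to set these against the efforts it asks for.

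**Inputs.** Muscle Strength Testing: 6 paired manoeuvres, 2 arms, 5 recorded repetitions (grip and practice repetitions not counted; each flexion/extension-type pair counted once). Power output: 3 bouts. Training text: 9 exercises. Schedule: 3 sessions a week for 12 weeks, with removal below 10 completed sessions in a six-week period.

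**Counts.**
- Recorded isokinetic repetitions per visit: 6 × 2 × 5 = 60. Of these, 2 × 2 × 5 = 20 are forearm and wrist movements.
- Over Visits 1, 2 and 3: 3 × 60 = 180.
- Ergometer bouts over Visits 1 and 3: 2 × 3 = 6.
- 1RM tests and exhaustion holds at Visit 1: 9 of each, if every exercise is tested once.
- Training sessions for a subject who is not removed: 10 + 10 = 20 at least, 3 × 12 = 36 at most.

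| Occasion | Efforts at or near maximum | Readings described beforehand | Rules tied to a value |
|---|---|---|---|
| Visit 1 | 3 bouts, 60 repetitions, 9 1RM tests, 9 holds | 0 | 0 |
| Visit 2 | 60 repetitions | 0 | 0 |
| Visit 3 | 3 bouts, 60 repetitions | 0 | 0 |
| Each of 20–36 sessions | 2 sets of 9 holds | Collected, time not stated | 0 |

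**Stops and withdrawals.** One in-session safety stop is written, and a complaint triggers it. The stop when a hold passes 60 seconds (Training Intensity Assessment and Adjustments) is a loading rule that raises the weight for the next session. The pregnancy rule works before or between sessions. None uses a blood pressure or heart rate value.

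**The case against.** The strongest reply is that several layers already protect these subjects. Entry requires a physician's release specifically for high-intensity resistance training, and a history of cardiorespiratory events excludes. At Visits 2 and 3 an intake form asks about changes in health on the day. The trainer spots and cues, a physical therapist (PT) monitors sessions, and the senior staff meet the trainer at least weekly and may modify procedures. Holds are meant to end at exhaustion without pain, the ergometer warm-up is self-paced, and extra rest is allowed in strength testing. The questionnaire and intake form are named but not reproduced, so a vital-signs field could exist there.

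Much of this stands. The safeguards lower the risk, and the text supports only the statement that no reading is described. Visit 2 is the weakest case, since it has no ergometer test and a third of its recorded repetitions (20 of 60) are forearm and wrist movements. But no safeguard, as written, supplies a measured value before exertion or tells staff what to do with one. The weekly review and the end-of-session reassessment come after the effort, and the latter concerns training intensity.

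A reader might infer more than this, in four ways:
- That the trial has no vital-sign monitoring. It has, in training sessions.
- That subjects are likely to be harmed. The documents give no rate of abnormal readings, so the counts show exposure only.
- That the hazard comes from injury level, because lesions from T2 down are eligible. The documents do not discuss blood pressure control by level, and the point does not rely on it.
- That efficacy results are affected. Nothing in the analysis uses these readings.

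**Conclusion.** The point stands as a participant-safety gap. No blood pressure or heart rate reading is described before maximal testing at any of the three lab visits, and no value recorded in the 20 to 36 training sessions requires action. A symptom-free subject with an abnormal reading could pass through either setting without a required response. The existing safeguards reduce this risk but do not remove it.

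The conclusion rests on the protocol text alone. If a form held elsewhere already requires a pre-test reading with limits, citing it would settle the point. The size of the risk is unknown. The change is worth making because it is cheap and alters what is done on the day. Confidence is medium.

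**What to change.** 1. With the cuff and oximeter already planned, take a seated resting blood pressure and heart rate before any exertion at Visits 1, 2 and 3 (at Visit 1, before the vibration screen), and before the warm-up of every training session.
2. Before the first subject, have the responsible clinicians set limits for blood pressure (high and low) and heart rate. If a reading is outside them and still is on a repeat about 5 minutes later, withhold that day's testing or session, notify the PT and the principal investigator (PI) the same day, and apply the existing physician check before resuming.
3. Amend the removal rule under Visit 3 so that a subject is not removed when the shortfall below 10 completed sessions is due only to sessions withheld for this reason. The rule counts completed sessions, so merely not calling these sessions missed would not protect anyone. Log them separately; the covariate in the Statistical Plan should still count completed sessions only.
4. Rebook a withheld Visit 3 test as early as possible and record the days since the last training session.

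**Cost.** A short amendment and no new device. At 3 minutes per reading (assumption, range 2–4), the time per subject is 60–108 minutes over 20–36 sessions (range 2 × 20 = 40 to 4 × 36 = 144), plus 6–12 minutes over three lab visits. It is close to nil in training if the planned reading is simply taken before the warm-up. Each session has room: 90 − 65 = 25 to 90 − 60 = 30 minutes. The 5-minute repeat adds to this only when needed.

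**Downside.** If 5–10% of sessions raised an alarm (assumption), 18 × 0.05 = 0.9 to 18 × 0.10 = 1.8 sessions would be lost per six weeks. If each physician check took a week (assumption), the loss could reach about three times that, 2.7 to 5.4. A full attender can lose 18 − 10 = 8 before removal, but someone attending 12 can lose only 2, hence item 3. Postponing Visit 3 lengthens the untrained gap, because exercise still ends at 12 weeks, hence item 4; a visit already late in the 12–14 week window has little room.

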Primary outcomes: Increased peak isokinetic muscle torque output as measured using a Biodek machine of the shoulder internal rotators, external rotators, shoulder abductor/adductors, and shoulder flexion/extension, elbow flexion/extension, forearm pronation/supination, wrist flexion/extension, and hand grip measured using a handheld dynamometer at 6 weeks (mid-way into training) and 12 weeks (end of training) when compared to baseline.

Secondary outcomes:

- o Propulsion testing: Increased maximum speed and acceleration attained, peak force, and mechanical effective force measured using the SmartWheel during start-up propulsion over level and inclined surfaces at 12 weeks when compared to baseline
- o Transfer testing: Higher maximum and minimum attainable transfer heights to a height-adjustable transfer station at 12 weeks when compared to baseline;
- o Reduced upper limb pain across all joints (as recorded on the Numerical Rating Scale (NRS) and shoulder pain reported during activities (Wheelchair Users Shoulder Pain Index (WUSPI)) at 6 weeks and 12 weeks when compared to baseline;
- o Increased self-perceived aspects of health and function as measured using the Short Form SF-36 Walk Wheel scale at 6 weeks and 12 weeks and when compared to baseline.
- o Increased peak power and average power output at 12 weeks compared to baseline.

Specific Aim 2) Assess subjects' perceptions of the effectiveness of the vibration dumbbell training program

Hypothesis 2) Subjects will report a high level of satisfaction with the training on factors of efficiency, tolerance, perceived strength and functional benefits.

Study Design and Methods

Each subject will be asked to come to HERL three times over a 12-week study period. During these visits the following activities will take place a) Pain and Health Surveys (Baseline and Weeks 6, and 12), b) Muscle Strength Testing (Baseline and Weeks 6 and 12), c) Functional Testing (Baseline and Week 12), and Pre-Training Assessment and Instructions (Baseline). The 12-week Training Phase will start after Visit 1

Data will be collected electronically using redcap, or on paper as needed.

Visit 1 (Initial Visit)

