training upper limb muscle force and power. For any subject who begins training at 30 Hz, the frequency will be reassessed at each training session to progressively increase him/her (in increments of 5 Hz) to 40 Hz.

The vibrating dumbbell, without added weights, weighs 6 pounds. It is possible that early in the exercise program a subject in the vibration intervention group may not be able to properly perform a specific exercise with that weight. In this case the subject will perform the exercise with a lighter weight standard dumbbell until they increase sufficiently in strength.

Visit 1 will take up to 5 hours to complete.

Optimally, each subject will be scheduled for three training sessions per week in their home for 12 consecutive weeks. Although the home was chosen for the training setting to make it easier on subjects to comply with the protocol, training can take place in another location based on subject convenience. The training equipment is portable and can be easily setup and broken down after each session. All the training for both the control and vibration groups will be supervised by a trainer with appropriate knowledge of proper exercise form and safety. The trainer will travel to the agreed upon location and guide the subject through each training session. The training sessions will be monitored by a physical therapist (PT). Both the trainer and PT will be masked to subjects' performance on outcome measurements.

Prior to beginning each exercise session, female subjects will be reminded that they should not participate in vibration exercise activities if they are pregnant and should notify the study team if they think they could be. Female subjects will be asked weekly if they are or could be pregnant and this will be documented. If pregnancy is a possibility, the subject will be offered an over the counter pregnancy test. Subjects will be given the test to perform themselves, unless they are physically unable to because of disability related functional limitations. In these circumstances, a female staff member will assist as needed. Any subject reporting or testing positive for pregnancy will be withdrawn from the study.

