Training intensity will be adjusted progressively with add-on dumbbell weights that will be added to the vibrating dumbbell. Subjects will be asked to hold onto the vibrating dumbbell tightly for as long as they can for each exercise. If they are unable to hold on tightly for at least 15 seconds, the weight for the next session will be decreased, whereas if they are able to hold onto the dumbbell for greater than 60 seconds, the trainer will stop the exercise and the dumbbell weight will be increased for the next session. The amount of weight increased and decreased will be determined by the trainer and will be reviewed and verified by a member of the senior study personnel.

The trainer will meet with the senior study personnel (PT and PI) at minimum once a week to review subjects' training progress, performance, any complications, concerns or complaints that the subject expresses, and any changes in the health status of the subjects who had been seen over the course of the week. Senior personnel will re-assess and modify the training procedures as appropriate.

During the last week of training (week 12), the trainer will give subjects a survey to assess satisfaction with the training program to collect their feedback on factors such as tolerance, perceived strength, performance and health benefits, efficiency of training, choice to continue training, and if they would recommend this form of exercise to others.

The follow-up outcome assessment visit, which take place at our laboratory, will be conducted by the PhD student and overseen by the PI.

Visit 2 (midway visit)

Participants will come back to the lab 6-8 weeks from the beginning of the intervention. The follow-up visit intake form will be completed to identify any changes in the participants health or medical status, lifestyle or any other changes that could impact the participants ability to complete the exercise program. At this visit we will test their strength in the same way that it was tested on initial visit. Additionally, they will fill out the pain measure forms, the health and satisfaction form and the carpal tunnel questionnaire that were filled out at the first visit.

This visit is expected to take no more than 2 hours to complete.

Visit 3 (end of the exercise program)

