At the end of the 12-week intervention period, subjects will come back to the lab for the final visit. This visit will be scheduled 12-14 weeks after the start of the intervention. However, even if a participant is unable to come back at 12 weeks exactly, the exercise program will still end at 12 weeks.

The follow-up visit intake form will be completed to identify any changes in the participants health or medical status, lifestyle or any other changes that could impact the participants ability to complete the exercise program. At this visit subjects will complete all the measures that were completed during the first visit. This includes the pain measures, measure of health and function, carpal tunnel questionnaire, strength, power output and functional measures. These tasks are expected to take up to 5 hours to complete.

As stated above, three exercise sessions will be scheduled each week. We expect that this schedule will be modified due to scheduling conflicts, illness, etc. and it is possible that subjects may sometimes complete less than three visits per week. All visits that are changed or missed will be documented in the research record but will not be considered protocol deviations so long as they are completing a minimal number of sessions (10) per six-week period. If a subject completes less than 10 exercise sessions in a 6-week period they will be removed from the study.

As stated above, testing sessions at the HERL lab will be scheduled at 6 and 12 weeks from the baseline visit. We expect that this schedule will be modified due to scheduling conflicts, illness, etc. For this reason, subjects will be given a 2-week window (6-8, 12-14 weeks) in which to complete these visits. Testing sessions within this window will not be considered protocol deviations.

Eligibility Criteria

Inclusion Criteria:

- (1) have a neurological impairment secondary to a SCI or disease at T2 or lower
- (2) greater than 6 months post injury
- (3) use a manual wheelchair as primary means of mobility (at least 30 hrs. per week)
- (4) 18 to 65 years of age
- (5) provide signed medical release by primary care physician to engage in a high-intensity resistance training exercise program
- (6) live within 60 minutes driving time (1 hour) from the research center
- (7) able to perform a transfer independently to and from a wheelchair
- (8) have normal range of motion in the upper limbs.

Exclusion Criteria:

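### Aim 2 is surveyed once, in week 12, so starters who leave earlier never rate the training and the result is likely biased upward by an unknown amount

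*Combined protocol and SAP*

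**What the plan says.** Specific Aim 2 concerns how subjects perceive the training programme. Its hypothesis is directional: "Subjects will report a high level of satisfaction with the training on factors of efficiency, tolerance, perceived strength and functional benefits".

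The instrument and its timing appear under Training Intensity Assessment and Adjustments: "During the last week of training (week 12), the trainer will give subjects a survey to assess satisfaction with the training program". The listed content includes tolerance, perceived benefits, efficiency, willingness to go on training and willingness to recommend it.

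Two kinds of selection come before that survey.

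- **Before training.** Under Pain and Health Measures, the Vibration Tolerance paragraph sets a screen: "Participants will hold the dumbbell at 25Hz for 30 seconds with their arm at a forty-five-degree angle away from their bodies". On failure: "If they are unable to complete the assessment they will not be permitted to continue the study".
- **During training.** The plan is that "each subject will be scheduled for three training sessions per week in their home for 12 consecutive weeks". The section on Visit 3 adds: "If a subject completes less than 10 exercise sessions in a 6-week period they will be removed from the study". The description of the training sessions says: "Training procedures will be stopped immediately by the trainer if a subject complains of pain or extreme discomfort during the exercises". A physician check is then needed before training resumes. The same description withdraws subjects who become pregnant.

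One other form mentions satisfaction. For the midway assessment the protocol says: "they will fill out the pain measure forms, the health and satisfaction form and the carpal tunnel questionnaire that were filled out at the first" (that is, Visit 1).

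The Statistical Plan names strength, pain, quality of life, power, transfer ability and propulsion for the repeated measures ANCOVA. It does not name satisfaction or tolerance. Only its general promise of descriptive statistics for all variables could cover the survey.

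**The concern.** A survey given only in the final training week reaches only those still training then. The protocol foresees several ways out before that point. Some of them, such as pain, discomfort or poor attendance because the programme is a burden, are plausibly linked to what the survey asks about. Nothing described in the plan recovers the views of those subjects or says how their absence is handled.

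At stake is what Aim 2 can claim. A completer figure describes people who finished 12 weeks. Read as the acceptability of the programme to those who began it, it would probably be too favourable, and the tolerance item is the most exposed. The strength, pain and functional outcomes of Aim 1 are not part of this point.

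**Working it through.** The documents give no sample size, dropout rate, screen-failure rate or threshold for high satisfaction, so there is no planned figure to reproduce. What can be done is to bound the effect.

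**Inputs**

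- From the protocol: three sessions a week, hence 3 × 6 = 18 scheduled per six weeks, with removal below 10. The rule therefore tolerates attendance down to 10/18 = 55.6% and removes only low attenders.
- Assumed: s, the share satisfied among week-12 responders (90%); d, the share of starters lost before week 12 (0% to 40%); s_L, the share of those lost who would have been satisfied (0 to 1).

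**Formula**

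Satisfaction among all starters = s(1 − d) + s_L·d. The completer figure s exceeds this by d(s − s_L). The bias is upward only if leavers are less satisfied than responders (s_L < s), and it grows in proportion to the loss.

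**Results with s = 90%**

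| Loss d | All leavers dissatisfied (s_L = 0) | Leavers half as often satisfied (s_L = 45%) | All leavers satisfied (s_L = 1) |
|---|---|---|---|
| 0% | 90% | 90% | 90% |
| 10% | 0.90 × 0.90 = 81% | 0.81 + 0.45 × 0.10 = 85.5% | 0.81 + 0.10 = 91% |
| 20% | 0.90 × 0.80 = 72% | 0.72 + 0.45 × 0.20 = 81% | 0.72 + 0.20 = 92% |
| 40% | 0.90 × 0.60 = 54% | 0.54 + 0.45 × 0.40 = 72% | 0.54 + 0.40 = 94% |

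The worst-case overstatement is thus 9 points at 10% loss and 18 points at 20% loss. In the intermediate case it is 4.5 and 9 points.

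**Why the denominator is starters**

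Adding screen failures widens the range. With 10% failing the screen and 20% later loss, responders are 0.90 × 0.80 = 72% of those screened, and the range becomes 0.90 × 0.72 = 64.8% to 64.8% + 28% = 92.8%. That is not a satisfaction figure, because people who fail the screen never receive the programme and have no satisfaction with it to report. For satisfaction, the starter-based range is the relevant one.

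**Whether the midway form fills the gap**

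The Visit 2 text says its satisfaction form was also completed at Visit 1, which precedes all training, and the Visit 1 description contains no such form. It therefore cannot clearly be a rating of the training. Even if it were, it would miss anyone who left before Visit 2.

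**The case against.** The strongest reply is that the size is unknown and may be small. With little loss the effect is slight, and at 10% loss even the worst case of 81% might still be called high. That stands. A reader might infer that a favourable result is largely built in, or that Hypothesis 2 can hardly fail. The documents do not support either, since every rate behind such a statement would be assumed and the ranges above extend past 90% as well as below it. If the hypothesis is hard to fail, the lack of any threshold for a high rating is at least as much the reason. That is a separate gap, which an exit survey would not close.

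A reader might also infer that the screen biases the satisfaction rating. It is one 30-second hold at 25 Hz, whereas training uses 40 Hz at 60% of the one-repetition maximum, held to muscle exhaustion, over 12 weeks. Passing it does not ensure tolerance of the programme and says little about efficiency, strength or function. Nor is difficulty at 40 Hz an exclusion, because the protocol provides a 30 Hz start with reassessment at each session. Scoring such subjects as intolerant would contradict that pathway.

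Leavers need not be dissatisfied. Pregnancy leads to withdrawal, and illness or scheduling conflicts can bring attendance below the removal limit. Treating every silent leaver as dissatisfied is a bound, not an estimate.

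The question on choosing to continue training may look odd when put only to those who continued. Asked in the last week, it most naturally means continuing after the study.

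Finally, session logs, trainer notes and the weekly review of complaints do capture some information on tolerance before a subject leaves. They help to explain departures but do not supply the ratings on which Hypothesis 2 rests.

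**Conclusion.** The point holds for subjects who start training. The plan surveys satisfaction and tolerance in those still training in week 12, foresees earlier exits, and describes neither an exit survey nor a rule for the missing ratings. The rating is likely biased upward, most directly on tolerance, on the assumption that leavers are on average less satisfied than finishers. The amount cannot be fixed from the documents. For illustration, with an assumed 90% of responders satisfied, the all-starters figure is 72% to 92% at 20% loss and 81% to 91% at 10% loss.

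The screen mainly limits the population to which the result applies. This is a modest weakness in a descriptive aim of an exploratory study, worth correcting because correction is cheap.

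**What to change.** 1. Offer the same survey at exit, on paper, by phone or through REDCap, to every subject who starts training and stops or is removed for any reason.
2. Report satisfaction over all starters beside the completer figure. Count leavers without a survey as not satisfied only in a bound labelled as worst case, and tabulate the reasons for leaving so that unrelated exits are visible.
3. Report separately how many attempted and how many failed the 25 Hz screen. Describe starts at 30 Hz as such, without classing them as intolerance.

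The Visit 2 text should also state what its satisfaction form is, since the Visit 1 description contains none.

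The cost is one short survey per leaver and some extra reporting. REDCap is already in use and the trainer already keeps session records, so no treatment procedure or extra staff is involved. The satisfaction figure may come out less favourable.
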